2. Determine differences in range of motion of the affected joint in the corticosteroid plus lidocaine group as compared to the corticosteroid alone group.
3. Determine differences in patient-reported outcome scores (VAS-pain, qDASH, PRWE, ASES, SF12, EQOL) in the corticosteroid plus lidocaine group as compared to the corticosteroid alone group.
4. Report patient characteristics associated with efficacy of addition of lidocaine to corticosteroid injectate for pain and ROM resolution (type of injury, affected joint, age, BMI, comorbidities, etc.).

Hypotheses:

Hypothesis⁰: Corticosteroid injectate alone will result in statistically significant reduced pain scores as compared to corticosteroid with lidocaine for the treatment of tenosynovitis.

Hypothesis¹: Lidocaine plus corticosteroid injectate will result in equivalent requirements for repeat injection or conversion to surgery as compared with corticosteroid injectate alone for the treatment of tenosynovitis.

Hypothesis²: Lidocaine plus corticosteroid injectate will result in equivalent patient reported outcomes scores as compared to corticosteroid alone for the treatment of tenosynovitis.

Hypothesis³: Lidocaine plus corticosteroid injectate will result in equivocal patient-reported outcome scores, ROM, and pain reduction as compared to corticosteroid alone for the treatment of tenosynovitis.

Study Design

This will be a randomized control trial of a group of patients with upper extremity tenosynovitides treated with either lidocaine plus corticosteroid or corticosteroid injection alone by upper extremity fellowship trained surgeons at Emory University. Patients will be randomly assigned to one of two groups at the time of treatment: 1. Lidocaine Plus Corticosteroid and 2. Corticosteroid Alone. A random allocation sequence, concealed in consecutively numbered, opaque, sealed envelopes, determining active treatment or placebo, will be computer generated. Written-informed consent will be obtained from patients prior to injection.

Patients in the Corticosteroid group will be treated with a 40 mg/mL injection of corticosteroid following sterile preparation. The volume of injectate differs for each tenosynovitis being treated. For example, trigger finger patients in the corticosteroid alone group will receive a 1mL of injectate total (consisting of 1 mL of 40mg/mL triamcinolone).

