- Between the ages of 18 years and 95 years.

- For trigger finger: patients with a diagnosis of stenosing tenosynovitis based on a history of triggering and the presence of tenderness over the A1 pulley upon clinical examination. All patients, based on the Quinnell grading of trigger finger see in the figure below, will be included.

Grade	Clinical findings (during flexion and extension)
0	Normal movement
I	Uneven movement
II	Actively correctable
III	Passively correctable
IV	Fixed deformity

Exclusion Criteria:

- Patients who are minors, vulnerable subjects, or who are not willing to consent to participate in the study.
- Allergies to glucocorticoids, current daily use of glucocorticoids or strong opioids (morphine, fentanyl, hydromorphone, ketobemidone, methadone, nicomorphine, oxycodone, and meperidine), severe diabetic neuropathy of the hand influencing pain perception, rheumatoid arthritis, and neurological or psychiatric diseases, potentially influencing pain perception.
- Subjects who, in the opinion of the investigator, may be non-compliant with study schedules or procedures.

Statistical Analysis:

Data will be stored on an excel spreadsheet. We will collect the name, medical record number, age at time of surgery, ethnicity, gender, BMI, presence of diabetes, Quinnell grading of trigger finger, smoking status, pre-injection VAS-pain, post-injection VAS-pain, 10 point likert scale, complications, and need for repeat injection or surgical release. It is possible that other variables may be added depending on analysis. Each variable will be used as a nominal variable when possible (e.g. smoking status) or a continuous variable if needed (e.g. VAS-pain, patient related outcome scores). For some statistical calculations we may break up the continuous variables in to ranges (e.g. Ages 15-20, 25-30). We will perform statistical analysis using unpaired, 2-tailed Student t test to compare means for normally distributed data, Kruskal-Wallis test to compare medians of non-normally distributed data, and chi-square test to compare proportions. Statistical significance will be interpreted as $P < .05$. Confidence intervals will be calculated with a confidence level of 95%.

Specifically, the 2 groups will be compared using the Mann-Whitney U test to analyze the difference between the post-injection VAS scores. The Wilcoxon sign-rank test will be used to test the difference between the treatment and control group for pain and patient related outcomes.

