The minimally clinically important difference (MCID) varies for each outcome measure. Therefore, for the purposes of a power analysis, we will use the VAS-pain at the time of injection as the primary outcome. A similar study was published in 2017 from Earp *et al.* comparing needle-free jet lidocaine for pre-corticosteroid injection anesthesia with simultaneous lidocaine and corticosteroid injection. Using the results of this study as a metric, for the purposes of our study, to determine a 1-point change in VAS (4.5 to 3.5) with the reported standard deviation of 2 (SEM

was 0.4, with 30 subjects in each group) in the Earp *et al.* study, the number needed to treat to detect a difference between the treatment and placebo group would be 63 [32]. Therefore, we aim for a sample size of 63 patients for each possible tenosynovitis described in the inclusion criteria.

In total, **we plan to enroll 1000 patients total into this study** when combining all possible tenosynovitides encountered at Emory. These outcomes will be feasible to obtain in a reasonable time frame given the high volume of patients treated for tenosynovitis of all types at Emory. Patients will be grouped together for analysis and also broken into subgroups for sub-analysis based on primary diagnosis for injection.

JMP Pro Software or SPSS will be used to analyze the data and perform the statistics.

Risks to participation

Risks to participation include breach of confidentiality from PHI used to conduct the study. Every effort will be used to scrub data when possible and to use subject numbers/unique identifiers when possible.

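### The Wilcoxon signed-rank test, a paired test, is named for comparing two independent arms and conflicts with the unpaired tests named beside it

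*Combined protocol and SAP*

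**What the plan says.** Study Design describes a parallel-group trial: "Patients will be randomly assigned to one of two groups at the time of treatment". Nothing in the document describes matching between arms, a crossover, or two treated sites per patient.

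Statistical Analysis then gives three instructions that bear on the same outcomes:

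- A general rule by distribution: "unpaired, 2-tailed Student t test to compare means for normally distributed data, Kruskal-Wallis test to compare medians of non-normally distributed data". Both are tests for independent groups.
- A specific sentence for one outcome: "the 2 groups will be compared using the Mann-Whitney U test to analyze the difference between the post-injection VAS scores". This too is an independent-groups test.
- Immediately afterwards: "The Wilcoxon sign-rank test will be used to test the difference between the treatment and control group for pain and patient related outcomes".

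Under Outcome Measures, pain is scored by VAS. The third objective counts VAS-pain among the patient-reported outcomes: "Determine differences in patient-reported outcome scores (VAS-pain, qDASH, PRWE, ASES, SF12, EQOL) in the corticosteroid plus lidocaine group". The power paragraph takes VAS-pain at the time of injection as the primary outcome.

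**The concern.** The signed-rank test ranks within-pair differences. Between two separately randomised groups there are no pairs, so the named test cannot be carried out without something the plan does not supply.

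The plan is contradictory here, not silent. Post-injection VAS falls under both the Mann-Whitney sentence and the signed-rank sentence, because the latter covers pain without exception. For qDASH, PRWE, ASES, SF12 and EQOL the general rule would be valid, but the sentence written specifically for those outcomes names the paired test. No statement says which instruction governs.

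An analyst who follows the text has three routes:

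- Pair patients by an arbitrary order, such as spreadsheet row, and drop the surplus when arm sizes differ.
- Pair each patient's scores before and after injection. This tests change over time and leaves the difference between arms untested.
- Decide that another test was meant, possibly after the data have been seen.

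The outcome used to size the trial is among those affected.

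**Working it through.** **1. The plan's own figure.** Inputs from the power paragraph are a difference of 1 point (4.5 v 3.5) and SD 2. Two-sided alpha of .05 comes from Statistical Analysis. Power of 80% and equal allocation are assumptions, as the plan gives neither.

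- Two-sample formula: n per arm = 2(1.96 + 0.8416)² × 2² / 1² = 2 × 7.849 × 4 = 62.8, so 63. This matches the plan's 63, read as per arm.
- One-sample (paired) formula with SD of differences 2: 7.849 × 4 = 31.4, so 32 pairs. This does not match.
- The SD of 2 is a within-group SD, taken from a standard error with 30 subjects in each group, so the calculation is a two-sample one. The design and the sample size therefore both point to an unpaired analysis.

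**2. Why arbitrary pairing does not inflate error.** For two unrelated patients the SD of the difference is 2√2 = 2.83. The one-sample formula then gives 7.849 × 8 = 62.8, again 63 pairs. Pairing strangers neither gains nor loses much on average, but the result depends on who is paired with whom.

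**3. Can the arms be paired one to one?** The plan says the sequence is generated by computer but not by what method. Under assumed simple 1:1 randomisation, the probability of equal arms is C(N, N/2)/2^N, and the expected absolute difference in arm size is close to √(2N/π). The exact values are:

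| Total N | P(arms equal) | Mean number left unpaired |
|---|---|---|
| 63 | 0 (odd) | 6.4 |
| 126 | 7.1% | 8.9 |
| 1000 | 2.5% | 25.2 |

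**4. Does the verdict depend on the pairing?** Simulated normal data, means 4.5 and 4.5 minus the difference, SD 2, two-sided P<.05, normal-approximation tests. Each data set was analysed under two random row orders. There were 40,000 data sets per cell (20,000 at 500 per arm). The table gives the share in which the two orders disagree on significance:

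| Patients per arm | Difference 1 | Difference 0.5 | No difference |
|---|---|---|---|
| 31 (63 read as a total, one dropped) | 11.6% | 7.1% | 3.2% |
| 63 | 7.6% | 8.4% | 2.8% |
| 500 (even split of 1000) | 0.0% | 1.4% | 2.4% |

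The first two rows are needed because the plan does not say whether 63 is per arm or in total: "we aim for a sample size of 63 patients for each possible tenosynovitis described in the inclusion criteria". With VAS rounded to whole numbers from 0 to 10 and 63 per arm (4,000 data sets), the shares are 6.2%, 7.4% and 2.1%.

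As an illustration, one simulated data set with 63 per arm gave signed-rank P values from 0.14 to 0.99 over 5,000 random pairings. Mann-Whitney gave a single value, 0.42.

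**5. Rejection rates at 63 per arm, signed-rank v Mann-Whitney.** No difference: 4.7% v 4.8%. Difference 0.5: 26.8% v 27.3%. Difference 1: 76.8% v 77.3%. Type I error and power are essentially unchanged.

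**The case against.** The strongest reply is that this is a slip of the pen for rank-sum, and that no one would pair unrelated patients by row. The error-rate results support a mild view, and the sample size is unaffected. Some verdict changes also follow from any change of test. At 63 per arm, one arbitrary signed-rank ordering disagrees with Mann-Whitney in 6.5%, 7.0% and 2.4% of data sets (differences 1, 0.5 and 0). Two valid tests, the unpaired t test and Mann-Whitney, disagree in 5.2%, 5.9% and 1.9%. Most of the first set is therefore what any switch of test produces. The unequal-arm figures rest on simple randomisation; permuted blocks would bring the arms close to equal, although dropout could unbalance them again. For post-injection VAS, a reader could let the more specific Mann-Whitney sentence govern.

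These points limit the size of the harm but do not remove the error. The benchmark concerns switching tests. It does not excuse a test whose P value changes with row order, which neither valid test does. A slip is plausible, but the text names a different procedure, and no sentence restricts it to change within patients. Letting the Mann-Whitney sentence govern post-injection VAS still leaves every other patient-reported score under the paired test. It is also not clear that VAS at the time of injection, the outcome used for power, is the same measurement as post-injection VAS.

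**Conclusion.** The concern holds. A paired test is specified for a comparison of independent arms, and it contradicts the independent-group tests named in the same section for overlapping outcomes. This should be corrected before analysis. It does not threaten the design or the sample size.

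The consequence is an analysis that two competent statisticians could carry out differently. If the sentence were followed by arbitrary pairing, significance would depend on row order in roughly 3% to 12% of data sets of the size planned for a single diagnosis, and in at most 2.4% of pooled data sets of 1000. Those figures assume normal data, SD 2, and the arm sizes shown. They describe one literal reading. The other reading, testing change within each arm, was not quantified; its cost is that the question about the arms goes unanswered. Error rates are not inflated.

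**What to change.** In the signed-rank sentence of Statistical Analysis, replace the test name with Wilcoxon rank-sum (Mann-Whitney U). It then agrees with the sentence before it. If signed-rank is wanted, confine it to describing change within each arm from before to after injection, and say so.

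Deleting the sentence would also remove the error, but the result is not identical: the scores other than post-injection VAS would then follow the general rule, with the t test or Kruskal-Wallis chosen by distribution. Naming the replacement is tidier because it fixes one test in advance.

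The cost is one word or one sentence, with no extra patients or data. For information, with normal data the Mann-Whitney test has relative efficiency 0.955, so 63 per arm gives about 78% power in place of 80%, and 80% would need 62.8/0.955 = 65.7, or 66 per arm. The plan already names Mann-Whitney for post-injection VAS, so for that outcome the correction adds no new cost.

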**Corticosteroid Injections for the Treatment of Common Upper Extremity Pathologies,
With or Without Lidocaine: A Randomized Control Trial**

NTC# NCT03704584

Date: 7/9/2019

Project Summary

Title of Study: Corticosteroid Injections for the Treatment of Common Upper Extremity Pathologies, With or Without Lidocaine: A Randomized Control Trial

Principle Investigator: [name] MD

Co-Investigators: [name], [name], [name] MD, [name] MD, [name]

Study Coordinators: [name], [name], [name], [name]

Version date: 7/9/2019

Lay Summary: A tendon is a type of tissue that connects your muscles to your bones. These tissues help control actions such as running, jumping, grasping, and lifting. Without tendons, you wouldn't be able to control the movement of your body. A protective layer known as synovium covers tendons. This sheath produces fluid, which keeps the tendon lubricated and moving properly. Inflammation or swelling of the sheath is known as tendon sheath inflammation or tenosynovitis. This condition is often treated with an injection into or around the sheath. This injection often consists of a corticosteroid with or without lidocaine. Corticosteroid are drugs that decrease inflammation and are given for a number of orthopaedic conditions to decrease symptoms of the underlying disease. Lidocaine is also a drug that blocks the pain response, although it only blocks it momentarily. Our study aims to determine if corticosteroid injection alone is as effective as corticosteroid combined with lidocaine for the relief of tenosynovitis of the upper extremity.

Precis/Abstract:

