This will be a randomized control trial to study the efficacy of a combined lidocaine and corticosteroid injection on pain, range of motion, and patient reported outcomes versus a corticosteroid injection alone for the treatment of common upper extremity tendinopathies and nerve entrapments that are often treated with a combination of these injectates. Patients will be assigned randomly to a control group (corticosteroid injection alone) or the treatment group (lidocaine plus corticosteroid injection). At the initial injection a 10-point likert scale prior to and after the injection will be administered. The patients will be followed up at 6 weeks after the injection, at which time the Visual Analog Scale for pain (VAS-pain), range of motion (ROM), and patient reported outcome data will be collected and any complications will be noted. Patients will also utilize a pain journal to track VAS-pain over the first 7 post-injection days. We hypothesize that those who receive lidocaine plus corticosteroid injection will be non-inferior in regards to pain, range of motion (ROM), failure of injection requiring surgery, and patient reported outcome scores compared with patients who received corticosteroid injection alone.

Background and Significance:

Tenosynovitis is a common ailment of the upper extremity resulting in pain around the affected joint due to injury to the tendon sheath. One of the most common manifestations of tenosynovitis is trigger finger. Trigger finger is an extremely common pathology encountered by primary care providers and hand surgeons. Reported incidence of 28 cases per 100,000 has been documented [1]. This entity occurs when the contents of the flexor tendon sheath do not fit cleanly

within the sheath, causing friction on movement of the fingers. Progression from a clicking or locking sensation to complete inability to flex or extend the finger (hence the designation “trigger finger”) occurs over the course of the disease. Therefore, triggering may not be initially noted on exam. Pain from this pathology can be experienced at the proximal interphalangeal joint, the metacarpophalangeal joint, or even the palm [2]. Reported increases in rates have been documented in diabetics, cases of repetitive trauma, those with renal and thyroid disease, and individuals with inflammatory conditions [3].

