The cause of trigger finger is poorly understood, with early studies identifying the condition as a form of tenosynovitis on histologic analysis. More recent studies have identified a lack of inflammatory cells, suggesting an abnormality in proliferation of fibrocartilage rather than a primary inflammatory condition [4]. Treatment of trigger finger has been studied extensively, but few evidence based guidelines exist for the treatment of this disease process [1]. Current treatment modalities are diverse and numerous, including non-operative management (splinting, stretching techniques, heat therapy, electric stimulation therapy, acupuncture, corticosteroid injection, and high-intensity focused ultrasound aimed at degrading the fibrosis surrounding the tendon sheath) and operative management (with open, percutaneous, and endoscopic methodology all having been described) [1, 5]. In 2017, Amirfeyz *et al.* proposed an evidenced based treatment guideline for trigger finger, with the first line treatment listed as “steroid and local anesthetic injection” followed by open operative management upon either failure of corticosteroid injection or patient refusal of corticosteroid injection [1].

This treatment algorithm reflects existing research regarding treatment of trigger finger: corticosteroid injection for trigger finger has been studied extensively [6-25]. However, few well, randomized control trials have been undertaken comparing corticosteroid injection to placebo. Of the trials that have been done, both studies indicated improved outcomes with a combined injectate of corticosteroid with lidocaine versus just lidocaine alone [26, 27]. The long term efficacy of steroid injection is reasonable, with success rates as high as 69% [8]. That said, many patients will experience return of their symptoms and will go on to need open surgical treatment for recurrent trigger finger [3].

While several studies have compared corticosteroid injection with lidocaine to lidocaine injection alone, to date, no study has evaluated the effectiveness of a corticosteroid injection either with or without lidocaine. Our study aims to evaluate whether or not lidocaine in the injectate combined with corticosteroid improves patient reported outcomes and recurrence of pain and morbidity from trigger finger as compared with corticosteroid injection alone.

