In addition, similar pathologies exist where the role of lidocaine remains vague. One such pathology is de Quervain tenosynovitis. de Quervain tendinopathy affects the abductor pollicis longus (APL) and extensor pollicis brevis (EPB) tendons in the first extensor compartment at the styloid process of the radius. It is characterized by pain or tenderness at the radial side of the wrist. Although de Quervain tendinopathy is often attributed to overuse or repetitive movements of the wrist or thumb, the cause is generally unknown. It most commonly affects women between the ages of 30-50 years old [28].

A small randomized trial found that glucocorticoid injections resulted in significantly better symptom improvement compared with placebo one week after injection [29]. Among those who responded to glucocorticoid injections, the beneficial effects were maintained during the 12-month follow-up period. Another randomized trial also found that splinting plus glucocorticoid injection was better than splinting alone [30]. Most patients experience pain relief after a single glucocorticoid injection [30, 31]. In patients with recurrent symptoms after initial relief with the

first glucocorticoid injection, a second injection may provide benefit. However, limited evidence is available about the role of lidocaine during these injections. We further aim to elucidate the role of corticosteroid and lidocaine versus corticosteroid alone in the treatment of de Quervain tenosynovitis.

Furthermore, the role of lidocaine with corticosteroid in the treatment of a number of other tenosynovitides remains ambiguous. These include tenosynovitis of the shoulder, biceps, elbow, wrist, thumb, carpometacarpal, midcarpal, elbow, and small joints of the hand (PIP, DIP, MP). We aim to ascertain whether the corticosteroid and lidocaine injectate together is as effective as corticosteroid in the treatment of these tenosynovitides. For all these pathologies corticosteroid with or without lidocaine is standard of care for orthopaedic hand and shoulder surgeons and the use of either treatment regimen is based on personal preference by the surgeon.

Objectives:

1. Determine differences in pain scores / likert scale at the time of injection and during follow up in the corticosteroid plus lidocaine group as compared to the corticosteroid alone group.

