As stated above, the first line treatment for trigger finger is corticosteroid injection with lidocaine, although there are a significant proportion of hand surgeons who inject corticosteroid alone. As no study has evaluated the efficacy of lidocaine mixed with the injectate versus corticosteroid alone, our study does not constitute deviation from current status quo of best medical practice for the treatment of trigger finger. **Both treatment options are considered standard of care and it is solely based on physician preference for which regimen is chosen as an injectate.** Patients will be notified of any potential risks with signed written consent as they would before any standard corticosteroid injection for the treatment of trigger finger. They will also be asked to sign an additional consent form agreeing to participate in our study outlining the nature of the study and the fact that no deviation from current best medical practice will occur throughout the course of the study.

Benefits to future subjects or science

By identifying whether or not lidocaine combined with corticosteroid injectate leads to improved patient outcomes as compared with corticosteroid injection alone, we will be able to educate physicians and patients on best medical practice for treatment of trigger finger. Additionally, as lidocaine has been reported to cause significant burning during injection, if there is no additional benefit to addition of lidocaine to corticosteroid injection, we will be able to spare future patients the discomfort of combining the injectate with lidocaine.

Data safety and monitoring plan:

Patients will be followed up closely in clinic at 2 weeks and 6 weeks post-injection to ensure patients did not experience side effects from the injection and to assess for efficacy of the injection. A low dose of corticosteroid and lidocaine is being utilized and we do not anticipate adverse effects.

Patients will have the ability to remove themselves from this study either completely or partially, and these options will be elucidated on the written consent form.

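### The only primary, powered outcome is pain at injection; the effectiveness aims have no designated endpoint, no power statement and no non-inferiority margin

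*Combined protocol and SAP*

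**What the plan says.** The Lay Summary puts the question as whether "corticosteroid injection alone is as effective as corticosteroid combined with lidocaine for the relief of tenosynovitis of the upper extremity". The Abstract hypothesises that "those who receive lidocaine plus corticosteroid injection will be non-inferior in regards to pain, range of motion (ROM), failure of injection requiring surgery" and patient-reported scores, and places a visit at 6 weeks with VAS-pain among the measurements. For trigger finger, Background and Significance asks whether adding lidocaine "improves patient reported outcomes and recurrence of pain and morbidity from trigger finger as compared with corticosteroid injection alone". For the other diagnoses it says "We aim to ascertain whether the corticosteroid and lidocaine injectate together is as effective as corticosteroid in the treatment of these tenosynovitides". The Hypotheses section adds equivalence on repeat injection or surgery and on patient-reported scores. The Data safety and monitoring plan assigns the assessment of efficacy to the 2-week and 6-week visits.

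Pain at injection is also a declared interest. Objective 1 reads "Determine differences in pain scores / likert scale at the time of injection and during follow up", and the section on benefits to future subjects notes that lidocaine may burn on injection.

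Only the sample-size text in Statistical Analysis names a primary outcome: "for the purposes of a power analysis, we will use the VAS-pain at the time of injection as the primary outcome". The reason given is that minimally important differences vary between measures. The calculation is for a 1-point difference (4.5 to 3.5) with SD 2 and gives 63. Total enrolment is 1000, analysed pooled and by diagnosis. No margin is stated for any outcome.

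**The concern.** The powered outcome and the effectiveness aims concern different things. Pain at the time of injection can reflect the needle, any burning, and an anaesthetic block that the Lay Summary itself calls short-lived. None of these shows whether the tenosynovitis has improved weeks later.

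The stated reason does not settle the choice. Varying minimally important differences could favour VAS over the functional scores. They do not favour VAS at injection over VAS at 6 weeks, which is the same 0 to 10 scale.

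There is a second gap. The sizing is for a two-sided test of difference, whereas the aims are worded as equally effective, non-inferior or equivalent. Without a margin, a non-significant result at any time point would not support those words.

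At stake is the use of the result. The benefits section intends to advise physicians on practice according to whether the combination "leads to improved patient outcomes as compared with corticosteroid injection alone". As written, that advice would rest on unranked comparisons across several instruments, time points and diagnoses, each judged at P < .05.

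**Working it through.** **The plan's own figure.** Inputs from Statistical Analysis: difference 1, SD 2, two-sided 5%. Power and allocation are not stated; 80% and 1:1 are assumed.

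n per arm = 2 × (1.96 + 0.8416)² × SD² / difference² = 2 × 7.849 × 4 / 1 = 62.8, so 63 per arm.

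The figure reproduces as a number per arm, and it covers only a difference in VAS-pain at injection.

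**What each aim has in the plan.**

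| Aim | Primary status | Power statement | Margin |
|---|---|---|---|
| Pain at injection (part of Objective 1) | yes | yes, for a difference | none |
| Pain at follow-up (Objective 1, Abstract) | no | no | none |
| Patient-reported scores (Abstract, Objective 3, Hypotheses 2 and 3) | no | no | none |
| Repeat injection or surgery (Abstract, Hypothesis 1) | no | no | none |

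**What 1000 patients can show at 6 weeks.** The documents give no 6-week SD, dropout rate or margin. Assumptions:
- 1:1 allocation: 1000 / 2 = 500 per arm.
- 20% loss by 6 weeks: 500 × 0.8 = 400 per arm.
- SD 2 to 3. The plan uses 2 at injection; its quoted SEM of 0.4 with 30 per group implies 0.4 × √30 = 2.19.
- One-sided 2.5%, which matches the plan's 95% confidence intervals, and a true difference of 0.

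Power = Φ(margin / (SD × √(2/400)) − 1.96), with √(2/400) = 0.0707.

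| SD | Standard error | Power, margin 1.0 | Power, margin 0.5 |
|---|---|---|---|
| 2 | 0.141 | above 99.9% | Φ(3.54 − 1.96) = 94% |
| 2.5 | 0.177 | above 99.9% | Φ(2.83 − 1.96) = 81% |
| 3 | 0.212 | Φ(4.71 − 1.96) = 99.7% | Φ(2.36 − 1.96) = 65% |

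For 80% power at a 0.5-point margin the formula 2 × 7.849 × SD² / 0.25 gives 252, 393 and 566 per arm for SD 2, 2.5 and 3. The last exceeds 400, and also exceeds 500. With no loss at all, 500 per arm at SD 3 gives 75%.

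**A binary endpoint for comparison.** Take 69% success in both arms, an assumption borrowed from the upper long-term success rate quoted in Background. Then n per arm = 7.849 × 2 × 0.69 × 0.31 / margin². That is 336 for a margin of 10 percentage points and 1344 for 5. Reinjection or surgery would therefore be the more demanding choice if a tight margin is wanted.

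**The case against.** The strongest reply is that the trial does not have a single question. Pain at the time of injection appears in the first listed objective, the benefits section raises the discomfort of lidocaine, and Hypothesis 0 speaks of pain scores without a time point. This stands. A reader might infer that the powered test is irrelevant to the trial's purpose or cannot answer its question; the documents do not support that. It answers one declared objective and leaves the others without an endpoint.

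Nor do the documents show that the primary outcome is purely needle pain, carrying no information about the condition. Outcome Measures has VAS-pain assessed at rest and on active movement of the joint, and Statistical Analysis compares post-injection scores. The exact moment and task are not settled. On either reading, a score taken at the injection does not measure lasting relief.

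It may also be said that the primary outcome was chosen only as a convenience for sizing. In that case the trial has no designated primary outcome for any aim, and the same repair is needed.

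Two further points stand in part. VAS-pain at 6 weeks is one choice among several that the documents would allow; it is preferred here because it is scheduled for all patients, applies across diagnoses, and uses the scale already used for sizing. And the plan nowhere says that a comfort result will be presented as an effectiveness result, so that risk is one to close off, not a stated intention.

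**Conclusion.** The concern holds in this form: the effectiveness aims have no designated, powered endpoint and no margin, while the one powered outcome addresses comfort at injection. The defect lies in the designation of the endpoint and the missing margin more than in the total size.

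A reader might infer that more patients are needed, or conversely that 1000 are enough whatever the margin. Neither follows. Under the assumptions shown (1:1 allocation, 20% loss, true difference 0, one-sided 2.5%), the pooled trial is comfortable for a 1-point margin. At 0.5 points its power runs from about 94% down to 65% as the SD goes from 2 to 3. All of these inputs are illustrative, since the documents give none of them for 6 weeks. The conclusion about the missing endpoint and margin does not depend on them.

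**What to change.** In Statistical Analysis:
1. Designate pooled VAS-pain at 6 weeks as the endpoint for the effectiveness aim. State whether it is the rest or the movement score, and how patients reinjected or operated on before 6 weeks enter the analysis.
2. Analyse it as non-inferiority. State the direction, because the Lay Summary asks about steroid alone against the combination and the Abstract asks the reverse. Justify a margin, and give the rule that the 95% confidence limit on the unfavourable side must exclude it.
3. Report power at the planned 1000 patients for that margin, with stated SD and loss.
4. Keep VAS-pain at injection as the endpoint for the comfort aim. Put the two tests in a fixed order, decided before any data are seen.

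In the benefits section, state that a result on injection pain alone supports a conclusion about comfort, not about effectiveness.

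The cost is protocol wording and one power statement, with no new visit or measurement. No extra patients are needed at a 1-point margin; a smaller margin may need more if the SD is near 3. The drawback is that one outcome takes second place: if the first test in the order fails, the second is not formally tested.
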